4.2 Treatment Group Names and Labels

Statistical output will be presented by treatment group and the treatment labels to be used in the tables, listings and figures are defined in the table below.

Treatment Code Number	Treatment Group Description	Treatment Group Label, which will appear in the TLFs
Treatment A	100mg OD of COQUN ORAL FORMULATION	Group A
Treatment B	100mg BID of COQUN ORAL FORMULATION	Group B

	Form	Form No.	1M-DMST-011-01-A1
	Statistical Analysis Plan	Page	Page 11 of 69
		Effective Date	07/05/2018

4.3 Visit Names and Labels

The names to be used in the analysis datasets and the labels to be used in the tables, listings and figures for the different study visits are defined below.

Visit number	Visit name	Visit label, which appear in TLFs
V1-H0	Visit 1: assessment moment 0 (before COQUN intake)	Visit 1 – Hour 0
V1-H1	Visit 1: assessment hour 1	Visit 1 – Hour 1
V1-H2	Visit 1: assessment hour 2	Visit 1 – Hour 2
V1-H4	Visit 1: assessment hour 4	Visit 1 – Hour 4
V1-H8	Visit 1: assessment hour 8	Visit 1 – Hour 8
V1-H12	Visit 1: assessment hour 12	Visit 1 – Hour 12
V2	Visit 2 - Day 0	Visit 2
V3	Visit 3 - Day 7	Visit 3
V4	Visit 4 - Day 14	Visit 4
V5	Visit 5 - Day 28 (EOS)	Visit 5

4.4 Study periods, Baseline and Endpoint Values

- First date of medication administration

Day 1 date (collected in patients' V2-V5 diary) will be treated as first intake of study medication.

- Last date of medication administration

Day 28 date (collected in patients' V2-V5 diary) will be treated as last intake of study medication (if the subject completes the study this date should coincide with the date of last investigational product intake).

If the date of last intake of study medication is not available, due to premature termination or other reasons, date of last investigational product intake (collected in the end of study form of the CRF) will be imputed.

- Duration of study medication treatment

Duration (days) = Date of last medication administration - Date of first medication administration + 1

- Baseline value

The baseline value for a variable is defined as the last non-missing value collected before first study medication administration. In the single dose phase, the moment 0 (visit 1- hour 0) will be considered as baseline value while in the multidose phase, baseline will be visit 2 (day 0) if not specified otherwise.

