12.9 Analysis of Safety Variables

12.9.1 Adverse Events

	Study Title	Bioavailability Study of COQUN ORAL FORMULATION (CoQ10) administered in Healthy Adults (CoQ10-01)		
	Study ID	VF-BAQ10/2018	Sponsor:	VISUFARMA SpA
	Date	March 03, 2018	Vers.	Final

Safety will be monitored through vital signs, physical exams, clinical laboratory tests (hematology) and adverse events including assessment of relationship to the IP.

Analysis of safety will be performed on the safety set.

The recorded adverse events will be coded according to MedDRA. The adverse events will be summarized by treatment, System Organ Class, preferred-term and intensity.

Nature, incidence and intensity, as well as the investigator's and the sponsor's causality assessment will be reported for each treatment-emergent adverse event. Descriptive summary statistics, e.g., with regard to the incidence of symptoms and the causality assessment, will be presented for the period between V1-V5. Furthermore, all non treatment-emergent adverse events during pre-treatment will be reported between the ICF signature and the first IP intake at V1.

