5.1.4 Compliance to Study Treatment and Procedures

Collected Variables

Compliance to the treatment:

- Was the investigational product delivered to the subject? [CRF - Visit 2] (yes/no)
- Was the investigational product taken correctly? [CRF - Visit 3, 4, 5] (yes/no)

Compliance to the study procedures:

- Was the subject fasting for at least 10 hours before IP intake? [CRF - Visit 1] (yes/no)
- Was the investigational device taken by the subject? [CRF - Visit 1] (yes/no)
- Was the blood sampling taken? [CRF - Visit 1, 2, 3, 4, 5] (yes/no)
- Was the V1-V2 DIARY given to the subject? [CRF - Visit 1] (yes/no)
- Was the V1-V2 DIARY checked and retrieved from subject? [CRF - Visit 2] (yes/no)
- Was the V2-V5 given to the subject? [CRF - Visit 2] (yes/no)
- Was the V2-V5 given back to the subject? [CRF - Visit 3, 4] (yes/no)
- Was the V2-V5 DIARY checked? [CRF - Visit 3, 4, 5] (yes/no)
- Was the investigational product retrieved from subject? [CRF - Visit 5] (yes/no)
- Was the V2-V5 retrieved from subject? [CRF - Visit 5] (yes/no)

Derived Variables: Not applicable

Imputations for missing values: Not applicable

Analysis Sets to be used for:	Tables	Safety analysis set
	Listings	Safety analysis set
	Figures	Not applicable

Compliance will be summarized as follows:

Table 6. Compliance to Investigational Product (Safety set)

Compliance to the treatment will be presented by treatment group using default frequency statistics. The percentage of subjects will be calculated relative to the total number of subjects in Safety analysis set. Subjects with missing data will be presented as part of a "Missing" category.

Table 7. Compliance to The Study Procedures (Safety set)

Compliance to the study procedures will be presented by treatment group using default frequency statistics. The percentage of subjects will be calculated relative to the total number of subjects in Safety analysis set. Subjects with missing data will be presented as part of a "Missing" category.

Compliance variables will be presented in subjects data listings as follows:

Listing 7. Treatment Compliance

Treatment compliance data from CRF will be presented as a subject data listing.

Listing 8. Compliance to study procedures [1]

Compliance to study procedures will be presented as a subject data listing.

Listing 9. Compliance to study procedures [2]

	Form	Form No.	1M-DMST-011-01-A1
	Statistical Analysis Plan	Page	Page 17 of 69
		Effective Date	07/05/2018

Inclusion/Exclusion criteria

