5.1.8 Prior and Concomitant Medication

Medications will be reported as recorded in CRF.

Collected Variables:

- Medication generic name (text) [CRF – Cumulative Concomitant Medication Form]
- Dose administered [CRF – Cumulative Concomitant Medication Form]
- Unit (standard dosage units, e.g., mg, mcg, cc, mL, IU, etc.) [CRF – Cumulative Concomitant Medication Form]
- Frequency (categories: od=once daily / bid=twice daily / tid=3 times daily /qid=4 times daily / 5/day=5 times daily /prn= as required; etc) [CRF – Cumulative Concomitant Medication Form]
- Dosage form (categories: tab= tablet; cap = capsule, oint = ointment, supp = suppository, aer = aerosol, susp = suspension, spray, patch, syrups, drops, vials, gel, cream, etc.) [CRF – Cumulative Concomitant Medication Form]

	Form	Form No.	1M-DMST-011-01-A1
	Statistical Analysis Plan	Page	Page 20 of 69
		Effective Date	07/05/2018

- Route of administration (categories: os= oral / iv= intravenous / sc= subcutaneous / im= intramuscular / inh= inhalation / top= topical/ sl= sublingual/ oth= other) [CRF – Cumulative Concomitant Medication Form]
- Indication [CRF – Cumulative Concomitant Medication Form]
- Start date of medication [CRF – Cumulative Concomitant Medication Form]
- Stop date of medication [CRF – Cumulative Concomitant Medication Form]
- Medication ongoing (yes, no) [CRF – Cumulative Concomitant Medication Form]

Derived Variables:

- **Prior medications** are defined as those starting and ending prior to the first administration of investigational study medication.
- **Concomitant medications** are defined as medications started at or after first administration of investigational study medication and include medications started prior to the first administration of investigational study medication but continued during the study.

Imputations for missing values: Not applicable

Analysis Sets to be used for:	Tables	Safety analysis set
	Listings	Safety analysis set
	Figures	Not applicable

Concomitant and prior medication will be summarized by treatment group as follows:

Table 12. Concomitant and Prior Medication (Safety set)	The number of subjects with at least one concomitant/prior medication will be presented by default summary statistics, where the percentage of subjects is calculated relative to the total number of subjects considered valid for the safety analysis set.
--	--

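### SAP 4.4 dates first intake from the multidose diary, so medication that ended between the Day -7 dose and diary Day 1 is classed as prior

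*SAP*

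**What the plan says.** SAP 4.4, under the date of first medication administration, says that the Day 1 date from the V2-V5 diary "will be treated as first intake of study medication". The sentence carries no restriction to one phase. The matching sentence for the end of treatment is "Day 28 date (collected in patients' V2-V5 diary) will be treated as last intake of study medication", and the duration rule is "Duration (days) = Date of last medication administration - Date of first medication administration + 1".

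SAP 5.1.8 uses the first-administration date to sort medications. Prior medications "are defined as those starting and ending prior to the first administration of investigational study medication". Concomitant medications are those that start at or after that point, or that start earlier and continue. The footnotes of Table 12 repeat both definitions. Neither place has a separate rule for the single-dose day or the wash-out week.

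The protocol puts the first dose earlier. Under 10.6.10 each subject swallows one 100 mg capsule at the site on Day -7 under supervision. Section 12.9.1 reports pre-treatment events as those arising "between the ICF signature and the first IP intake at V1". SAP section 6 declares no change from the protocol's analysis.

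**The concern.** The date that SAP 4.4 calls first intake is not the first intake. It falls a week or more after every subject has been dosed. Because SAP 5.1.8 depends on that date, medication used only between the Day -7 capsule and the start of the multidose diary is reported as if it had been used before any exposure.

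The plan expects such records. Protocol 10.5.1 gives subjects a diary for V1 to V2 and asks them to note any treatment taken for an adverse event. Protocol 10.6.8 documents concomitant medication on Day -7 and again at Day 0. A reader of Table 12 who wants to know what subjects took after their first capsule would get an undercount of concomitant use and an overcount of prior use.

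**Working it through.** **Inputs.** First intake in the SAP: diary Day 1 (SAP 4.4). Actual first dose: Day -7 (protocol 10.6.10 and 12.9.1). Last intake: diary Day 28 (SAP 4.4). V2 is study Day 0 (SAP 4.3). The documents do not say whether diary Day 1 is study Day 0 or study Day 1, so both are shown as assumptions.

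**Step 1: the plan's own figure.** Duration = last - first + 1 = 28 - 1 + 1 = 28 days. This equals the stated length of the multidose phase, so the formula is correct for that phase alone.

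**Step 2: the shift in the first date.**
- If diary Day 1 is study Day 0, the shift is 0 - (-7) = 7 days. Diary Day 28 is study Day 27, and the span from first to last dose is 27 - (-7) + 1 = 35 days.
- If diary Day 1 is study Day 1, the shift is 1 - (-7) = 8 days. Diary Day 28 is study Day 28, and the span is 28 - (-7) + 1 = 36 days.

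**Step 3: the medication rule.** With whole-day dates, and D for the study day of diary Day 1, the SAP calls a medication prior when its stop day is before D. Measured from the real first dose, it is prior when its stop day is before Day -7. The two labels differ exactly when the stop day is on or after Day -7 and before D, whatever the start day. Running every start/stop pair from Day -30 to Day 28 through both rules gives:

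| Pattern | Mislabelled, D = Day 0 | Mislabelled, D = Day 1 |
|---|---|---|
| Starts and stops from Day -7 to the day before D | 28 of 28 | 36 of 36 |
| Starts before Day -7, stops in that window | 161 of 161 | 184 of 184 |
| Starts in that window, still in use on D or later | 0 of 203 | 0 of 224 |

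All other pairs receive the same label under both rules. These are combinations of dates that show how the rule behaves. They do not forecast how many records will be affected.

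**Step 4: where the date is used.** The split feeds Table 12 (subjects with any prior and any concomitant medication) and the P/C status in Listing 12. Listings 2 and 19 have treatment-day fields whose origin is not stated, so they may also use it. No planned table summarises exposure duration. SAP 4.4 sets baseline by phase, at hour 0 of Visit 1 and at Visit 2. Tables 18 to 23 present adverse events by phase.

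**Step 5: size in Table 12.** The table counts subjects, so a mislabelled record changes a count only when it is the subject's only entry in a category, or falsely becomes the first. If all 12 subjects of an arm are in the safety set, one subject moves a percentage by 100/12 = 8.3 points.

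**The case against.** The best defence is that SAP 4.4 means the multidose phase: the date comes from the multidose diary, and the duration formula returns the right 28 days for it. That is probably what was intended, and the duration stands on that reading. But the sentence does not say so, SAP 5.1.8 refers simply to first administration, and the same section of the SAP does distinguish the phases for baseline. Without that limit, the medication split goes wrong.

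A second defence is that a drug used only in the wash-out is not taken alongside the product, which is how protocol 9.8 describes concomitant medication. However, 9.8 restricts medication over the whole study, and 10.6.8 keeps what was taken before screening apart from what is documented from Day -7 onward. SAP 5.1.8's own test is first administration, not continuous dosing.

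It is also fair that few records may be affected. Subjects must be free of prescribed medication, and Listing 12 shows start date, stop date and indication, so wash-out use stays visible whatever its label. The documents give no expected count.

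Four stronger readings are tempting, and the documents do not support them:
- *The last-intake date is also wrong and adds an undosed day.* This requires diary Day 28 to be the V5 date, which is not stated. If diary Day 1 is study Day 0, diary Day 28 falls the day before V5. Even otherwise, the protocol flow chart marks product intake at V5. For early terminators, when the date is unavailable, SAP 4.4 falls back on the end-of-study form.
- *The protocol-violation review would be misled.* SAP 5.1.3 reviews potential violations case by case and does not use the prior/concomitant flag. Treatment of an adverse event is expressly allowed by protocol 9.8.
- *Baselines or the PK results are affected.* The per-phase baseline sentence prevents this.
- *One fifth of the study is misclassified in all 24 subjects.* Seven of 35 days describes a calendar window, not affected records. Only medications that ended inside it change label.

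**Conclusion.** Wrong as written, of minor severity. SAP 4.4 contradicts protocol 12.9.1 on when first intake occurs, and SAP 5.1.8 then mislabels every medication that ended on or after Day -7 and before diary Day 1. The window is 7 days if diary Day 1 is study Day 0, and 8 if it is study Day 1. The effect is confined to the prior and concomitant counts in Table 12, the status flag in Listing 12 and, if they count from the same date, the treatment-day fields in Listings 2 and 19.

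The conclusion rests on reading SAP 4.4 and 5.1.8 literally and on whole-day dates. A medication stopped on Day -7 itself cannot be placed before or after the capsule from dates alone; it is counted here as on study. How many records fall in the window cannot be known from the documents, and could be none.

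**What to change.** In SAP 4.4, define first administration as the date of the V1 (Day -7) dose, and state that SAP 5.1.8 and the footnotes of Table 12 use this date. Keep a separately named first multidose intake, equal to diary Day 1, for the 28-day multidose duration, and say which study day it is. Add to Listings 2 and 19 which of the two dates their treatment days count from.

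The cost is about two sentences in SAP 4.4 and a short note on the listings. The dates are already collected in the CRF and diaries, so no new data are needed. The SAP is to be signed before the database is locked, which leaves a natural point for the change. The change brings the SAP into line with the protocol, so it does not create a departure to declare in section 6.

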4.5 Visit Windows

Visit 1 is the screening visit: once the subjects are considered eligible for the study, all 24 adult healthy subjects will enter the single dose treatment phase and will be given a dose of 100 mg of COQUN ORAL FORMULATION and plasma coenzyme Q10 will be measured over the next 12 hours: at 1, 2, 4, 8 and 12 hours after intake.

	Form	Form No.	1M-DMST-011-01-A1
	Statistical Analysis Plan	Page	Page 12 of 69
		Effective Date	07/05/2018

After 7 days (Visit 2 – Day 0), subjects will return at site for entering the multidose phase and will be randomly divided into two groups of treatment.

After 7, 14, and 28 days Visit 3, Visit 4, Visit 5 (EOS) will be performed respectively.

4.6 Coding Systems and Conventions

4.6.1 Coding of adverse events and medical history

Adverse event and medical history investigator terms will be presented in TLF as recorded in CRF. Any coding will be used upon request.

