14.4 Data Management

The statistical evaluation of the clinical study data is performed by CRO using the statistical software package SAS version 9.4.

The investigator will enter the data in the respective CRF sections.

After data are entered into the database, they will be checked according to a pre-specified Data Validation Plan. All numeric data, coded entries, tick boxes, and date fields will be checked automatically for plausibility, completeness, and validity. Verbatim entries (e.g. concomitant medication, AEs) will be provided in special data listings and cross-checked by appropriately trained staff at CRO. Questions, errors, and missing data found will be collected in Data Query Forms and sent to the investigator for clarification. Returned query forms will be checked for correctness, resolved queries will be entered to the study database and unresolved or new queries will be returned to the investigator. This process will be repeated until all queries are resolved. Finally, the responsible data manager will lock the database.

Verbatim entries (AEs, prior or concomitant diseases, and medication) will be coded by means of the following internationally accepted systems:

	Study Title	Bioavailability Study of COQUN ORAL FORMULATION (CoQ10) administered in Healthy Adults (CoQ10-01)		
	Study ID	VF-BAQ10/2018	Sponsor:	VISUFARMA SpA
	Date	March 03, 2018	Vers.	Final

- Adverse events: MedDRA
- Concomitant medication: WHO Drug Reference List
- Concomitant diseases and diagnoses: MedDRA

For further details refer to the Data Management Plan filed in the TMF of this study.

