5.2.2.1 Adverse Events

Collected Variables:

- Event, i.e. diagnosis or signs/symptoms (text) [CRF – Cumulative adverse event form]
- The start and stop date of the event [CRF – Cumulative adverse event form]
- Outcome of event (categories: recovered/resolved, recovered/resolved with residual effects, recovering/resolving, not recovered/ not resolved, fatal, unknown) [CRF – Cumulative adverse event form]
- Severity (categories: mild, moderate, severe, life threatening or disabling) [CRF – Cumulative adverse event form]
- Treatment (categories: none, specific drug treatment, specific non drug treatment) [CRF – Cumulative adverse event form]
- Relationship with study device (categories: definitive, probable, possible, unlikely, none) [CRF – Cumulative adverse event form]
- Action taken with study device (categories: none, dose reduction temporarily, dose reduced, discontinued temporarily, discontinued) [CRF – Cumulative adverse event form]
- Pattern (categories: every study drug administration, intermittent, continuous, other) [CRF – Cumulative adverse event form]
- Seriousness (yes, no) [CRF – Cumulative adverse event form]

Derived Variables:

- Adverse Events (AEs): an adverse event is any untoward medical occurrence in a subject or clinical study subject administered a pharmaceutical product and which does not necessarily have a causal relationship with this treatment. An AE can therefore be any unfavourable and unintended sign, symptom, or disease temporarily associated with the use of a medicinal product, whether or not considered related to the medicinal product. The definition covers the entire study period, independent of whether IP was administered or not.
- Serious adverse event (SAEs): Any untoward medical occurrence or response to a medicinal product that at any dose: results in death, is life threatening, results in in-subject hospitalization or prolongation of existing hospitalization, results in a persistent or significant disability/incapacity, is a congenital anomaly/birth defect or, important AEs that are not immediately life-threatening or do not result in death or hospitalization but may jeopardize the subject or may require intervention to prevent one of the other outcomes listed.

	Form	Form No.	1M-DMST-011-01-A1
	Statistical Analysis Plan	Page	Page 25 of 69
		Effective Date	07/05/2018

In the analysis serious adverse events will be identified by the variables "Seriousness" (yes, no).

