- Related AEs: in the analysis related AEs will be defined as AEs for which the relationship with study device is assessed as "definitive" or "probable" or "possible"
- Severe AEs: in the analysis severe AEs will be defined as AEs for which the severity is assessed as "severe" or "life threatening"
- Subjects who prematurely terminated the Study Due to AE: in the analysis subjects who prematurely terminated the study due to AE are defined as those subjects with an adverse event for which the reason for early termination in the CRF end of study has been recorded as "adverse event"
- Death: death is defined as a fatal outcome of an AE.

Adverse events (AEs) will be reported on a per-subject basis. This implies that even if a subject reported the same event repeatedly, the event will be counted only once. In the latter case, the event will be assigned the worst severity and strongest relationship to the investigational study medication. The presentation of AEs is therefore restricted to the incidence per subject of AEs assigned to the Treatment Period.

Analysis Sets to be used for:	Tables	Safety analysis set
	Listings	Safety analysis set
	Figures	Not applicable

Adverse events will be summarized by default summary statistics by treatment group. Percentages will be calculated relative to the total number of subjects considered valid for the Safety analysis set.

Table 18. Summary of Adverse Events in the Single Dose Phase (Safety set)

Overview of AEs in the single dose phase including the:

- number of subjects with at least one AE.
- number of subjects with at least one device-related AE.
- number of subjects with at least one serious AE.
- number of subjects with at least one severe AE.
- number of subjects who prematurely terminated the study.
- Number of AEs
- Number of serious AEs
- Number of related AEs
- Number of severe AEs
- Number of deaths

Table 19. Summary of Adverse Events in the Multidose Phase (Safety set)

Overview of AEs in the multidose phase including the:

- number of subjects with at least one AE.
- number of subjects with at least one device-related AE.
- number of subjects with at least one serious AE.
- number of subjects with at least one severe AE.
- number of subjects who prematurely terminated the study.
- Number of AEs
- Number of serious AEs
- Number of related AEs
- Number of severe AEs
- Number of deaths

	Form	Form No.	1M-DMST-011-01-A1
	Statistical Analysis Plan	Page	Page 26 of 69
		Effective Date	07/05/2018

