6. CHANGES TO THE ANALYSIS AS LAID DOWN IN THE PROTOCOL AND AMENDMENTS

No changes to the analysis as laid down in the protocol were made.

1MED Regulatory & Clinical Development	Form	Form No.	1M-DMST-011-01-A1
	Statistical Analysis Plan	Page	Page 31 of 69
		Effective Date	07/05/2018

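### The SAP makes MedDRA coding of adverse events optional and drops the protocol's SOC/preferred-term summary without declaring the change

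*SAP*

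**What the plan says.** Protocol 12.9.1 is firm on both coding and presentation: "The recorded adverse events will be coded according to MedDRA", and then "The adverse events will be summarized by treatment, System Organ Class, preferred-term and intensity". Protocol 14.4, on the coding of verbatim entries, repeats the dictionary: "Adverse events: MedDRA". Neither section makes coding optional.

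SAP 4.6.1 reads differently: "Adverse event and medical history investigator terms will be presented in TLF as recorded in CRF". The only mention of coding that follows is "Any coding will be used upon request". It names no dictionary, no version, no deadline and no person who would make the request. SAP 5.2.2.1 collects the event as free text.

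SAP 5.2.2.1 also sets a per-subject rule, under which "even if a subject reported the same event repeatedly, the event will be counted only once", keeping the highest severity and the closest causal link. The footnotes to Tables 22 and 23 apply the same idea. For Tables 20 and 21 the SAP gives an open-ended description of the special-interest events, and the table shells turn it into eleven named rows.

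Protocol 12.1 expects the SAP to explain any major deviation from the protocol's analysis. SAP section 6 says: "No changes to the analysis as laid down in the protocol were made".

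**The concern.** There are two separate problems.

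The first is a plain contradiction. The protocol promises coding and a specific summary. The SAP withdraws both by default and then states that nothing was changed. Someone who relies on section 6 would not know that the promised table is missing.

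The second is what the absence of a common term does to certain counts. Counting the same event once requires a way to decide that two entries are the same. Filling a row called Fatigue or Upper abdominal pain requires a way to decide which entries belong there. Preferred terms would settle both. With free text and no mapping rule, the decision falls to whoever programs the table, in a study that is not blinded (SAP 2.6). Both secondary objectives concern safety and tolerability, so these tables carry the secondary results.

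**Working it through.** The plan states no figure on this point, so there is none to reproduce. The check sets the two documents side by side and then adds one piece of arithmetic.

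**Step 1. Protocol requirement against SAP content.**

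| Protocol requirement | SAP content |
|---|---|
| MedDRA coding of AEs (12.9.1, 14.4) | Verbatim terms, coding on request (4.6.1) |
| Summary by treatment, SOC, preferred term and intensity (12.9.1) | No such table among Tables 18 to 23 |
| Major deviations explained in the SAP (12.1) | None declared (section 6) |

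**Step 2. What the six AE tables show.**

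- Tables 18 and 19: overall counts by arm for each phase, with no term.
- Tables 20 and 21: eleven named special-interest terms by arm and in total, one table per phase.
- Table 22: by relationship, with no term.
- Table 23: by severity, with no term.

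Tables by SOC or preferred term: 0 of 6. Tables of all AEs by term and arm: 0 of 6. Tables of a fixed subset of terms by arm: 2 of 6. An AE outside the eleven rows is therefore shown by term only in the listings. Listing 18 gives every AE with its treatment group.

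**Step 3. Which counts can depend on wording.**

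- *Not exposed:* in Tables 18 and 19, the numbers of subjects with at least one AE, serious AE, severe AE or related AE. Having any AE record is enough for the first. The others come from the CRF fields for seriousness, severity and relationship. Merging two records at the higher severity and closer relationship cannot change whether a subject has at least one.
- *Exposed:* the same-event rule in Tables 22 and 23. Suppose, as an illustration, that one subject has a mild entry of tiredness and a moderate entry of fatigue. Treated as the same event, they put the subject under moderate only. Treated as different events, they put the subject under mild as well.
- *Exposed if the once-only rule applies to them:* the rows of Tables 18 and 19 that count AEs rather than subjects.
- *Exposed:* assignment to the rows of Tables 20 and 21. No rule says whether tiredness belongs under Fatigue, or stomach ache under Upper abdominal pain.

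**Step 4. Size for a special-interest row.**

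Inputs: 12 subjects per arm and 24 in total (SAP 2.5), all assumed to be in the Safety set. The percentages use the number of subjects in the column as denominator.

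- One subject in one arm: 1/12 = 0.083, or 8.3 percentage points.
- One subject in the Total column: 1/24 = 0.042, or 4.2 percentage points.

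These are upper limits for one subject. The shift occurs only if the entry in question is that subject's sole event in the row; if the subject has another entry there, the shift is zero. For Table 20 the Total column is the natural one to read, because every subject takes the same single dose before randomisation.

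**The case against.** The strongest reply is that this is a small exploratory study with no pre-specified hypotheses. Listing 18 gives every AE with arm, severity, relationship, seriousness and dates, so 24 subjects' events could be tabulated by hand. That is fair, and it limits the importance of the point. It does not supply the summary that the protocol promised, and it does not make section 6 accurate.

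A second reply is that nothing in the SAP calls for literal string matching. The open description of special-interest events leaves room for medical judgement, and Protocol 14.4 has trained staff cross-check verbatim AE entries. This also stands. A reader might infer that the SAP prescribes counting synonyms as different events. It does not; it gives no rule, and miscounting is a risk that follows from the gap.

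A third reply is that SAP 4.6.1 governs what the outputs show. Coding might still be done under the Data Management Plan cited in Protocol 14.4, which is not among the documents. So it cannot be concluded that the database will be uncoded, only that the planned outputs use verbatim terms and that coding is left to an unspecified request.

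Two broader readings are also tempting. One is that no table shows any AE by term and arm; Tables 20 and 21 do so for eleven terms. The other is that all per-subject AE counts depend on wording; the at-least-one counts in Tables 18 and 19 do not.

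**Conclusion.** The point holds as an undeclared departure from the protocol. The SAP makes mandatory MedDRA coding optional, omits the table by SOC, preferred term and intensity, and declares no change. This is a stated rule that conflicts with the protocol, so it is more than a missing detail.

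The effect on results is real but limited. It is confined to the special-interest rows, the same-event rule in Tables 22 and 23, and any event counts made under the once-only rule. For a special-interest row, the most that one reclassified subject can do is 8.3 points in an arm or 4.2 points in total. This assumes full groups of 12 and that the entry is that subject's only one in the row. How often it would happen cannot be judged from the documents. The correction is desirable and cheap; the point does not threaten the study's main conclusions.

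**What to change.** 1. In SAP 4.6.1, restore MedDRA coding of AEs, state the version, and require coding to be complete before database lock.
2. Add a table of AEs by SOC, preferred term and intensity: by treatment for the multidose phase, and overall for the single-dose phase.
3. In SAP 5.2.2.1 and the footnotes to Tables 22 and 23, define the same event as the same preferred term within a subject and phase. Define each row of Tables 20 and 21 by a list of preferred terms.
4. Correct SAP section 6 so that it declares any departure that remains. Declaring the departure without the other steps would cure the disclosure gap but leave the matching problem in place.

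SAP 4.6.2 treats medications in the same way, against the WHO Drug coding in Protocol 14.4, and can be settled in the same edit.

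The AE changes cost the coding of what should be a small number of terms and one additional table shell per phase.
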